6.4.4. Lost to follow-up

A low "lost-to-follow-up rate" will be essential for the validity of the study. To minimize lost to follow-up, a multi-faceted follow-up process will be established, which is a four-level follow-up process. Level 1 activities include electronically sending the follow-up questionnaire and – in case of no response – two reminder emails. If Level 1 activities do not lead to a response, multiple attempts are to be made to contact the study participant, and the HCP by phone. In parallel to these Level 2 activities, searches in national and international telephone and address directories, as well as electronic social networks, are started (Level 3 activities). If this is not successful, an official address search via the respective governmental administration and commercial databases will be conducted. This Level 4 activity can provide information on new addresses (or emigration or death). The aim is to keep the total lost to follow-up at the end of the study at less than 15% of the study population. Study participants may want to withdraw from the study, and they are allowed to do so at any time. If possible, the reasons for study withdrawal will be collected.

Supporting document SOP PM01 - Doc PM3004.03

6.5. Study size

The sample size calculation is based on an incidence rate of 10 VTE (DVT of the lower extremities and PE) per 10,000 WY for EE/LNG. It is expected that E4/DRSP is associated with a VTE risk that is not higher than the risk associated with EE/LNG. The study should be powered to test the non-inferiority of E4/DRSP treatment regarding VTE risk in comparison to EE/LNG use.

At an incidence rate of 10 VTE per 10,000 WY, a total of 150 VTE cases could be expected within 150,000 WY. Sample size calculations show that approximately 150,000 WY of observation is statistically sufficient (power = 80%, $\alpha = 0.05$) to exclude a 1.5-fold VTE risk for E4/DRSP users compared to EE/LNG users. Calculations are based on a recruitment phase of 5 years, follow-up of 101,000 women (50,500 E4/DRSP users and 50,500 EE/LNG users) for 2 years, and a total drop-out and lost-to-follow-up rate of 15% (see Table 4).

Subsequent exclusion of users of higher-dose monophasic LNG containing COCs (more than 30µg EE/ more than 150µg LNG), estimated to represent only 0.15% of study participants (equals 230 women-years), will not significantly affect statistical power.

Statistical considerations regarding sample size.

However, observations from COC PASS studies finalized in the last 5 years suggest that the VTE incidence rate in a general population of COC users may be lower than the previously accepted 10 VTE/10,000 WY. The INAS-SCORE (NCT01009684), finalized in February 2017, observed an EE/LNG VTE incidence of 8.8 VTE/10,000 WY in European women and INAS-FOCUS (EUPAS1597), finalized in August 2020, observed an EE/LNG incidence rate of 7.9 VTE/10,000 WY within the USA study population. The recently finalised PRO-E2 study found an overall VTE incidence in LNG/EE users of 5.8 VTE/10,000 WY in the EU population and an incidence of 4.7 VTE/10,000 WY of the lower extremities and PE in the same study population. Anecdotal reports from physicians participating in INAS-SCORE and INAS-FOCUS, and PRO-E2 studies suggest that there is increased awareness regarding the risk of VTE associated with COC use. A change in prescribing practices by physicians due to increased risk awareness may be partially responsible for the change in risk incidence.

Therefore, with the assumption that 150,000 WY is the feasibility limit for a prospective, non-interventional study, it is possible to construct alternative scenarios based on a lower overall VTE incidence rate of 7.0 VTE/10,000 WY (Table 2).

Table 2: Sample size alternatives based on various assumptions.

Inc. COC _{LNG}	Inc. E4/DRSP	HR ₀	HR _{ni}	Expected #VTE	WY _{Total}	Power (%)
0.001	0.001	1	1.5	151	150,426	80%
0.0007	0.0007	1	2	105	150,000	97%
0.0007	0.0007	1	1.65	105	150,000	82%

Inc.: incidence of VTE; COC_{LNG}: Levonorgestrel-containing combined oral contraceptive; E4/DRSP: Estetrol/Drospirenone; HR: Hazard ratio; #VTE: Number of venous thromboembolisms; WY: Women-year

ZEG Berlin

Estetra Study Protocol

Supporting document SOP PM01 - Doc PM3004.03

Line 2 and 3 show that with a lower overall incidence of 7.0 VTE/10,000 WY, and pre-specified 150,000 WY of observation, the study would still have 97% power to exclude a 2.0-fold risk, and >80% power to exclude a 1.65-fold risk.

As an additional comment, our current working hypothesis is that E4/DRSP will have a slightly lower risk of VTE compared to currently available COCs, including EE/LNG. This assumption is based on results from clinical trials and comparative studies on coagulation biomarkers:

- The observed VTE incidence from the pooled Phase 2-3 E4 clinical program was 2.8 VTE/10,000 women (95% CI 0.7 15.6), with a 95% confidence interval based on Poisson distribution.
- The VTE incidence rate, in view of 2,735 WY of exposure, was 3.7 VTE/10,000 WY (95% CI: 0.9 20.4).
- Haemostasis parameters were investigated in Study MIT Es0001-C201 which concluded that E4/DRSP 15/3 mg was associated with -
 - Less resistance to activated Protein C (APC) than EE/LNG (change from baseline: +30% versus +165%)
 - Decreased change from baseline in F1+2 as compared with EE/LNG (+23% versus +71%)
 - o No statistically significant changes from baseline in coagulation inhibitors.
 - o No effect on soluble E-selectin

and therefore, a more neutral haemostatic profile.

- Overall haemostasis results indicate that E4/DRSP 15/3 mg has less effect on haemostatic parameters compared with EE/LNG 0.03/0.15 mg, and also less than observed with the COCs containing E2 [8, 9] and E2V. [10, 11]
- The VTE adjusted hazard ratio of E2V versus EE/LNG was observed as 0.4 (95% CI 0.2-1.1) in the INAS-SCORE PASS. [12].

Based on the above argumentation, it is worth considering a scenario with a less conservative margin choice, i.e., that E4/DRSP has a decreased risk of VTE compared to LNG-COC and the subsequent sample size calculations for the proposed PASS study could be modified accordingly (Table 3).

Table 3: Sample size calculations assuming differing incidence rates between cohorts.

Inc. COC _{LNG}	Inc. E4/DRSP	HR₀	HR_{ni}	Expected #VTE	WY _{Total}	Power (%)
0.0007	0.000561	0.8	1.5	95	150,000	92%

Inc.: incidence of VTE; COC_{LNG}: Levonorgestrel-containing combined oral contraceptive; E4/DRSP: Estetrol/ Drospirenone; HR: Hazard ratio; #VTE: Number of venous thromboembolisms; WY: Women-year

Supporting document SOP PM01 - Doc PM3004.03

For this sample size calculation, the assumption is that the feasibility limit for a prospective non-interventional study of COC is 150,000 WY. Assuming a hazard ratio of 0.8 and an EE/LNG VTE incidence of 7.0 VTE/10,000 WY, the study would have sufficient power to exclude a 1.5-fold risk with 92% power.

The proposed sample size for the investigation of the VTE risk is also sufficient for the evaluation of unintended pregnancy assuming an incidence between 0.5-0.8 per 100 WY (Pearl Index). However, acute myocardial infarction and stroke are very rare in a female population of reproductive age. This study is powered to exclude a 2.5-fold risk of ATE (a secondary outcome). This is sufficient to screen for safety signals.

Table 4 Expected observation time

Assumptions: approx. 101,000 study participants recruited over 60 months (~ 1,684 per month); follow-up of study participants 2 years; drop-out rate of 0.7% per month (e.g., 12 out of 1,684 recruited women will drop-out during the first month after recruitment; therefore, the average number of women during the first month is 1,678 women [(1,684+1,672) x 0.5]); LTFU, end of observation due to treatment stopping or switching, and dropout is expected with approx. 20%.

	Sub-cohorts recruited during the month					
Time after study start	1	2		60		
[month]	Average number of women in follow-up					
1	1,678					
2	1,666	1,678				
		1,666				
24	1,428	•••	***			
25		1,428				
26						
60				1,678		
82				1,438		
83				1,428		
WY	3,099	3,099	3,099	3,099		
Total WY (crude)	185,953					
Total WY (Corrected regarding treatment adherence, treatment stopping/switching, LTFU/dropout)	≈150,000					

ZEG Berlin

Estetra Study Protocol

Supporting document SOP PM01 - Doc PM3004.03

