The final analyses will include both an "as-treated" (AT) and an "intention-to-treat" (ITT) analysis. All eligible women will be assigned to the ITT and AT population at baseline. Only women with follow-up information will be considered for longitudinal analysis. Women who never started their prescribed baseline medication will be considered in the ITT analysis but excluded from the AT analysis. Population characteristics, e.g., socio-economic factors, parameters of reproductive, contraceptive history, and medical history, will be summarized descriptively and used to estimate the probability of treatment differences. Inverse probability of treatment weighting combined with time-to-event analysis of VTE will be carried out based on the extended Cox model to calculate hazard ratios (HR) with 95% confidence intervals. The null hypothesis to be tested is HR of VTE ≥1.5 (i.e., the VTE HR for E4/DRSP vs. EE/LNG is higher than or equal to 1.5). The alternative hypothesis is HR of VTE <1.5.

Milestones

Data collection is expected to start Q4/2022 after EMA approval of protocol and medical drug commercially available and is anticipated to end Q4/2028 after the start of data collection. The final study report will be available in Q2/2029.

Supporting document SOP PM01 - Doc PM3004.03

2. Amendments and updates

Number	Date	Section of study protocol	Amendment or update	Reason
None				

3. Milestones

Milestone	Planned date
Global Ethics Approval	Q4/2022
Registration in the EU PAS register	Q4/2022
Start of study	Q4/2022
Start of data collection (First Patient First Visit)	Q1/2023
Last regular follow-up ¹	Q3/2027
End of data collection (Last Patient Last Follow-Up)	Q3/2028
Annual report(s) ²	Annually (First report: Q2/2023)
Final report of study results	Q2/2029

EMA=European Medicines Agency, MA=Marketing Authorization, PRAC=Pharmacovigilance Risk Assessment Committee ¹Assumes last 20% of study participants followed for 12 months only.

4. Rationale and background

E4/DRSP is a novel oral contraceptive containing a fixed dose of E4 (14.2 mg) and DRSP (3 mg) which is taken for 24 days followed by 4 days of placebo. E4 is a natural estrogen, only produced during pregnancy by the foetal liver. When combined with the progestin DRSP, ovulation is inhibited. The E4/DRSP combination may have less impact on hepatic and haemostasis parameters in comparison to combinations of DRSP with ethinyl estradiol (EE) and ethinyl estradiol/levonorgestrel combination (EE/LNG) [1–3].

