6.1. Study design

This is a large, multinational, prospective, active surveillance study that follows two cohorts. The cohorts consist of new users (starters⁹ and restarters¹⁰) of two different groups of hormonal contraceptives: E4/DRSP and EE/LNG. The study will use a non-interference¹¹ approach to provide standardized, comprehensive, reliable information on these treatments in a routine clinical practice setting.

Study participants will be recruited via recruitment centres (health centres, pharmacies, telemedicine/online prescription services, and electronic medical records [see details in Section 6.2]) for the INAS-NEES study. An international network of COC-prescribing HCPs will recruit eligible COC-users over an estimated period of 5 years. After study entry, study participants will be followed for a maximum of 2 years for rare serious safety outcomes. Additional follow-up procedures (see Section 6.4.2) will be used to validate patient-reported events. A non-interventional approach will be used for the INAS-NEES study. Enrolment procedures should not interfere with the prescribing behaviour of the participating HCPs or with the individual needs of their patients. People prescribed a new COC are eligible to join the study provided they are prescribed a COC under investigation, sign an informed consent form (ICF), complete a baseline questionnaire, and understand the language of the ICF and questionnaires. Adolescents (below the age of 18 years) will be eligible to participate based on local legislation.

Through direct contact with the study participants at 6, 12, 18, and 24¹² months after enrolment, relevant clinical outcomes will be captured. However, because laypersons often over-report, or misclassify AEs (e.g., varicose veins as "thrombosis" or pneumonia as "pulmonary embolism"), patient-reported events of interest to the study will undergo careful validation. This will be accomplished by contacting the relevant HCPs (usually the treating physicians) and by reviewing medical documentation. Under routine medical conditions, clinical outcomes are not always

⁹ First-ever user of a COC

User who restarts hormonal contraceptive use with a COC (same COC as before or new COC) after an intake break of at least two months.

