6.6.2. Database freeze and lock

For each interim analysis (see Section 6.7.2) and for the final analysis, the database will be frozen at a predefined time point. The database will be 'cleaned' within 4 weeks of the database freeze.

Supporting document SOP PM01 - Doc PM3004.03

After the final database lock (approximately 4 months after the last follow-up questionnaires have been sent to the study participants), no additional incoming data will be entered into the database – this database will represent the final data source for all analyses. Safety copies will be made of each database to enable the calculations to be repeated if necessary.

Follow-up of information on pregnancy outcomes will continue after the final database lock. For information gathered after this final database lock, the database will not be reopened, and the information will only be used for pharmacovigilance purposes.

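### The abstract, milestone table, Section 6.2 and Table 4 give incompatible timelines, and Table 4 credits more follow-up than the protocol's own end-of-study rule allows

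*Protocol*

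**What the plan says.** Four places in the protocol fix the timeline.

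- **Sections 6.1 and 6.5.** Prescribers "will recruit eligible COC-users over an estimated period of 5 years". The size calculation uses the same period: "Calculations are based on a recruitment phase of 5 years, follow-up of 101,000 women (50,500 E4/DRSP users and 50,500 EE/LNG users) for 2 years". Table 4 assumes "approx. 101,000 study participants recruited over 60 months (~ 1,684 per month") and a "drop-out rate of 0.7% per month". It gives each monthly cohort 24 months and 3,099 WY, and the month-60 cohort runs to month 83. The crude total of 185,953 WY is then reduced to about 150,000, on the ground that "LTFU, end of observation due to treatment stopping or switching, and dropout is expected with approx. 20" per cent.
- **Section 6.2.** The follow-up phase closes about one year after the last woman is enrolled. Women enrolled in the last recruitment year stop at that point, before 24 months.
- **Section 3, milestone table.** First patient Q1/2023, last regular follow-up Q3/2027 (a footnote gives the last 20% of participants 12 months only), and "End of data collection (Last Patient Last Follow-Up") at Q3/2028.
- **Abstract.** Data collection starts in Q4/2022 and "is anticipated to end Q4/2028 after the start of data collection".

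**The concern.** These statements cannot all hold. Sixty months from Q1/2023 ends between the end of Q4/2027 and the end of Q1/2028, after the listed last regular follow-up. Even the later milestone, Q3/2028, leaves the last women 3 to 9 months of follow-up, where Section 6.2 promises about 12 and Table 4 counts 24.

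This bears on the size claim because Table 4 is the only support for 150,000 WY. Row 1 of Table 2 needs 150,426 WY for 80% power, and Section 6.5 calls 150,000 WY the feasibility limit, so there is no reserve. Months credited to late cohorts but never observed reduce the expected events and the power.

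**Working it through.** **Inputs (Section 6.5, Tables 2 and 4).** 1,684 women per month for 60 months; 0.7% monthly drop-out; 24-month cap; net factor 150,000/185,953 = 0.8067; 10 VTE per 10,000 WY in both arms; true HR 1; margin 1.5; 1:1 allocation.

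**1. Reproduce the plan.**
- WY per cohort = sum over k = 0 to 23 of 1,684 × 0.993^k × 0.9965 / 12 = 3,099.4 (stated 3,099).
- Times 60 = 185,965 crude (stated 185,953). Times 0.8067 = 150,009 net.
- Events needed = 4 × (1.645 + 0.842)² / (ln 1.5)² = 150.4, so 151, as in Table 2. This match needs one-sided 5%; a two-sided 5% gives 191. That is a separate matter, and one-sided 5% is kept here to isolate the effect of the dates.

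**2. Months available.**
- Table 4: 83.
- Section 6.2: 60 + 12 = 72.
- Abstract, Q4/2022 to Q4/2028: nominally 72 (69 to 75, depending on the days within the quarters).
- Milestone table, Q1/2023 to Q3/2028: 63 to 69.
- Q1/2023 to Q3/2027: 51 to 57.

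**3. Recompute with truncation.** If observation ends at month T, cohort m gets min(24, T − m + 1) months. For T = 72, cohorts 1 to 49 keep 24 months (49 × 3,099.4 = 151,871 WY) and cohorts 50 to 60 get 23 down to 13 months (26,053 WY). The total is 177,925 crude, and × 0.8067 = 143,524. Power = Φ(½ √events × ln 1.5 − 1.645). For 143.5 events this is Φ(0.784) = 78%.

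| 60 months of recruitment, observation to | Crude WY | Net WY | Events | Power |
|---|---|---|---|---|
| month 83 (Table 4) | 185,965 | 150,009 | 150 | 80% |
| month 72 (Section 6.2 rule) | 177,925 | 143,524 | 144 | 78% |
| month 69 (latest Q3/2028) | 173,082 | 139,618 | 140 | 77% |
| month 63 (earliest Q3/2028) | 159,827 | 128,926 | 129 | 74% |

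Spreading enrolment evenly within each month lowers the truncated rows slightly: 142,869 at month 72, and 127,794 to 138,806 at months 63 to 69.

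**4. How far this depends on the drop-out correction.** The crude total already loses 0.7% a month, and 1 − 0.993^24 = 15.5% by month 24. The further 20% again names loss to follow-up and dropout. Counting one 20% loss and no monthly loss:
- T = 72: (49 × 24 + 198) woman-months per monthly recruit × 1,684 / 12 = 192,818; × 0.8 = 154,254 WY.
- T = 69: (46 × 24 + 231) × 1,684 / 12 × 0.8 = 149,876 WY.
- T = 63: (40 × 24 + 270) × 1,684 / 12 × 0.8 = 138,088 WY.

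**The case against.** The best defence is that these are planning estimates. The recruitment period is called estimated, the one-year rule approximate and the milestones planned. A stand-alone milestone plan is to follow protocol approval (Annex 1), and Section 6.7.2 monitors accrual and rechecks the size assumptions. The abstract's nominal 72 months do hold 60 + 12, and the cost there is about 5% of the WY and under 2 points of power against a target stated as approximate. All of that stands, and it limits the size of the point. It does not make the abstract, Section 3, Section 6.2 and Table 4 agree.

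A reader might infer three stronger conclusions. The document does not support them.

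- **That 150,000 WY is missed on any reading.** It is not. Counting the 20% loss once, 60 + 12 months reaches about 154,000. Alternatively, enrolling all 101,000 women by Q3/2026 (39 to 45 months, about 2,240 to 2,590 a month) with 24 months each to Q3/2028 gives about 150,000. Each route gives up another stated figure: the first Table 4's two-step correction, the second the 60 months, the 1,684 a month and the 12-month footnote.
- **That observation stops at Q3/2027.** Closing recruitment at month 42 to 45 with 12 more months would leave about 98,500 to 106,000 WY. But the next row of the same table places last patient last follow-up at Q3/2028, and the last regular follow-up is not defined separately. So large a loss should not rest on that label.
- **That the Q2/2029 final report is unachievable.** Lock comes "approximately 4 months after the last follow-up questionnaires have been sent to the study participants". Counted from either stated end, Q3 or Q4/2028, this is compatible with Q2/2029. The report date comes under pressure only if the end of follow-up moves to Q1/2029, a date the protocol does not state.

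**Conclusion.** The inconsistency is in the text and does not depend on any modelling: the milestone dates cannot hold 60 months of recruitment plus 12 of follow-up, the listed last regular follow-up precedes the end of recruitment, and no stated dates supply Table 4's 83 months. Table 4 also gives 24 months to women whom Section 6.2 and the milestone footnote truncate.

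The effect on size is modest. On Table 4's own inputs and factor it is about 5% of the WY under the one-year rule (power about 78%), and about 7 to 14% if 60 months of recruitment is cut at Q3/2028 (about 74 to 77%). These figures assume even accrual at 1,684 a month, 10 VTE per 10,000 WY, one-sided 5%, and the 20% correction taken on top of monthly drop-out. The last assumption matters most: with the loss counted once, the one-year rule gives no shortfall, and the milestone dates give about 138,000 to 150,000 WY. The protocol should correct this, but it does not undermine the design.

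**What to change.** 1. Use one timetable in the abstract, Section 3, Section 6.2 and Section 6.5, and define the last regular follow-up relative to the end of data collection.
2. Recompute Table 4 with truncated follow-up for women enrolled in the last recruitment year. State whether the approximately 20% includes the 0.7% monthly drop-out or comes on top of it.
3. Then choose one of two courses. Either move the milestones to fit 60 + 12 months (from Q1/2023: last enrolment Q4/2027 to Q1/2028, last follow-up Q4/2028 to Q1/2029, with lock and report dates rechecked), or keep the dates and restate women, WY, expected events and power for the time available.

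The work is protocol wording and one recalculated table. The price is either later dates to agree with the regulator or slightly less favourable size figures.

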The combined oral contraceptive (COC) containing estetrol (E4) and drospirenone (DRSP) (E4/DRSP) is a novel oral contraceptive containing a fixed dose of E4 (14.2 mg) and DRSP (3 mg). E4 is a natural oestrogen only produced during pregnancy by the foetal liver. When combined with the progestin DRSP, ovulation is inhibited. The E4/DRSP combination may have less impact on hepatic and haemostasis parameters in comparison to combinations of ethinyl estradiol (EE) and levonorgestrel (LNG) or EE and DRSP. Yet, it is unknown whether this regimen has an impact on the cardiovascular risk associated with the use of hormonal contraceptives.

Research question and objectives

The primary objective of the study is to characterize and compare the risks of E4/DRSP with EE/LNG, in a study population that is representative of the actual users of these preparations. This includes an estimate of the absolute risk of rare serious adverse outcomes. The main clinical outcome of interest is venous thromboembolism (VTE), i.e., deep venous thrombosis (DVT) of the lower extremities and pulmonary embolism (PE). Secondary objectives include measuring the occurrence of unintended pregnancy, assessing the risk of arterial thromboembolism (ATE), describing the drug utilization pattern, describing the baseline risk profile for VTE and ATE, and investigating outcomes associated with foetal exposure to E4/DRSP.

Study design

Multinational, comparative, prospective, active surveillance study that follows two cohorts. The cohorts consist of new users (starters¹ and restarters²) of two different groups of hormonal

First-ever user of a COC

User who restarts hormonal contraceptive use with a COC (same COC as before or new COC) after an intake break of at least two months.

Supporting document SOP PM01 - Doc PM3004.03

contraceptives: E4/DRSP and EE/LNG. The study is taking a non-interventional³ approach to provide comprehensive information on these treatments in a routine clinical practice setting. Study participants will be enrolled via an international network of COC-prescribing health care professionals (HCPs) and then followed up for one to two years. All outcomes of interest will be captured by direct contact with the study participants. Reported outcomes of interest will be validated via attending physicians and relevant source documents. The classification of outcomes of interest into 'confirmed' and 'not confirmed' will be verified by blinded independent adjudication.

Population

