The study will be divided into 2 phases: the recruitment phase and the follow-up phase. The recruitment phase starts when the study participant is introduced to the study by the HCP (i.e., after a prescription has already been agreed upon), the signing of an ICF, and the completion of a baseline questionnaire (baseline survey). The follow-up phase includes direct follow-up with the study participant at 6, 12, 18, and 24 months after study entry. The follow-up phase will end approximately one year after enrolment of the last study participant. However, participants who are enrolled within the last year of the recruitment phase will have their last routine follow-up at the end of the follow-up phase (instead of 24 months after study entry). Visits and follow-up contacts are calculated in calendar months and years following the baseline visit. In keeping with German national regulations, the recruitment process will be modified for Germany. The description of the relevant modified passages is displayed in *Annex 3.3*.

HCPs will act as recruiters, identifying potentially eligible study participants, facilitating the onboarding process, educating study participants regarding the study expectations, and consenting them to participate in the study. There will be limited additional involvement from the recruiting HCP. Importantly, the role of HCPs in this PASS should be to act as a recruiter and point of contact for the collection of the study participant's safety information. The primary method of data collection will be through patient-reported outcome questionnaires. Study participants will be followed up by the ZEG Berlin study team independent of the recruiting

Supporting document SOP PM01 - Doc PM3004.03

HCPs. In the case a study participant will report an outcome of interest to the study, the recruiting HCP may be re-contacted to clarify health outcomes of interest reported by the study participant.

The following recruitment centres will be used:

1. Health centres

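### Table 4 credits every participant with 24 months of follow-up, but section 6.2 ends follow-up about a year after the last enrolment, so the roughly 150,000 woman-years are not derived from the design described

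*Protocol*

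**What the plan says.** Table 4 (section 6.5) takes "approx. 101,000 study participants recruited over 60 months (~ 1,684 per month" and assumes "follow-up of study participants 2 years; drop-out rate of 0.7% per month", illustrated by "12 out of 1,684 recruited women will drop-out during the first month after recruitment". Every sub-cohort column shows 3,099 WY, and the month-60 sub-cohort still contributes 1,438 and 1,428 women in months 82 and 83. The crude total is 185,953 WY. The next row reduces it to about 150,000 WY, labelled "Corrected regarding treatment adherence, treatment stopping/switching, LTFU/dropout", and the assumptions line puts that loss at roughly 20%. The text of section 6.5 confirms that the calculation follows all 101,000 women for 2 years.

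The design sections describe something shorter:

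- Section 6.2: "The follow-up phase will end approximately one year after enrolment of the last study participant", and "participants who are enrolled within the last year of the recruitment phase will have their last routine follow-up at the end" of that phase rather than at 24 months.
- Section 6.1, footnote 12: the last contact may come at study end if that falls before a participant's 24 months.
- Abstract, study design: participants are enrolled and "then followed up for one to two years".
- Section 3, Milestones, footnote 1: the final fifth of participants are assumed to have one year of follow-up.

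**The concern.** Women enrolled in the last recruitment year cannot supply the 24 months that Table 4 credits to them. Administrative truncation is not among the reasons given for the step from 185,953 to about 150,000 WY, so that correction does not cover it. Table 2 line 1 needs 150,426 WY for 80% power at margin 1.5. The planned yield therefore has no reserve, and any real loss of observation time takes the study below its stated power. The alternative scenarios in Tables 2 and 3 also use 150,000 WY as the available exposure.

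**Working it through.** **Inputs.** From Table 4: 1,684 women per month for 60 months, drop-out 0.7% per month, crude 185,953 WY, corrected about 150,000 WY. From section 6.5: 10 VTE per 10,000 WY, margin 1.5, true HR 1, 1:1 allocation, alpha 0.05. From section 6.2 and the Milestones footnote: the two follow-up rules.

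**1. Reproduce Table 4.** Average women in follow-up month k = 1,684 × 0.993^(k−1) × (1 + 0.993)/2. This gives 1,678 and 1,666 for months 1 and 2, and 1,438 and 1,428 for months 23 and 24, as printed. WY per sub-cohort = 1,678.1 × (1 − 0.993^24)/0.007/12 = 3,099.4. Times 60 = 185,965, against 185,953 stated. The crude total therefore contains no truncation. The correction factor is 150,000/185,953 = 0.807.

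**2. Reproduce the power.** One-sided Schoenfeld: power = Φ(√D × ln(1.5)/2 − 1.645). With D = 150.4, power = 80.0%, and 151 events are required, as in Table 2. The two-sided version needs 191 events, so the protocol's basis is one-sided 5%. I keep that basis below.

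**3. Apply the section 6.2 rule.** Sub-cohort m gets min(24, E − m + 1) months, where E is the last month of follow-up.

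- E = 71: crude 176,440 WY, ratio to full follow-up 0.949, corrected about 142,300 WY.
- E = 72: crude 177,925 WY, ratio 0.957, corrected about 143,500 WY.

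**4. Apply the footnote rule.** Twelve months of follow-up give 1,615.0 WY per sub-cohort. 48 × 3,099.4 + 12 × 1,615.0 = 168,151 crude WY, ratio 0.904, corrected about 135,600 WY.

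**5. Consequences** (events at 10/10,000; margin 1.65 at 7/10,000, where Table 2 states 82%):

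| Rule | WY | Change | Events | Power, 1.5 | Power, 1.65 |
|---|---|---|---|---|---|
| Table 4 | 150,000 | – | 150 | 80% | 82% |
| Section 6.2 | 142,300-143,500 | −4% to −5% | 142-144 | 78% | 80-81% |
| Footnote | 135,600 | −9.6% | 136 | 76% | 79% |

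The 97% for margin 2.0 falls to about 96%. The 92% in Table 3 falls to about 91% (section 6.2) or 90% (footnote).

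**6. Check the correction factor.** The crude total already loses 1 − 0.993^24 = 15.5% of each sub-cohort by 24 months, which matches the 15% total drop-out and loss to follow-up in section 6.5. The further reduction of about 20% names loss to follow-up and drop-out again. If that 20% is the whole loss and is deducted once:

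- No truncation: 1,684 × 60 × 2 × 0.8 = about 161,700 WY.
- Section 6.2 rule: about 152,900 WY (E = 71) to 154,300 WY (E = 72). With D = 152.9, power is about 81%.
- Footnote rule: 1,684 × (48 × 2 + 12 × 1) × 0.8 = about 145,500 WY. With D = 145.5, power is about 79%.

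**The case against.** The strongest reply is that Table 4 errs in both directions. Step 6 shows that a single deduction of drop-out would absorb the whole loss under section 6.2 and most of it under the footnote. This stands, and it limits what can be said about the net result. It does not validate the table: the protocol does not calculate the yield that way, and an unstated offset is a further reason to redo it.

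The larger loss rests on a Milestones footnote whose timetable does not fit Table 4. It is attached to a last regular follow-up in Q3/2027, while 60 months of recruitment from Q1/2023 would end around the turn of 2027/2028. The rule in the body text, section 6.2, costs only about 4-5% of the WY and about 2 points of power. That also stands.

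Section 6.7.2 plans interim reports that re-examine the sample size assumptions. They may reveal a shortfall in exposure, but the section names no action to follow.

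A reader might infer more than the documents support:

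- That the power above 80% for margin 1.65 fails. It fails only under the footnote rule.
- That Table 2 line 1 is wrong. It states what 80% power requires, and it is correct as such.
- That the abstract fixes the stop date. It gives only a range of one to two years.
- That power falls further when the upper limit of a two-sided 95% interval is used. That is a separate question about alpha and is not caused by the follow-up rule.

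**Conclusion.** The contradiction is certain: Table 4, section 6.2 and the Milestones footnote describe three different follow-up schemes. By Table 4's own drop-out rate and correction factor, the expected yield is about 4-5% too high under section 6.2 and 9.6% too high under the footnote. That costs about 2 or 4 points of power at margin 1.5, from a plan with no reserve.

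It does not follow that the study will fall short of 150,000 WY. That depends on whether the 20% reduction repeats drop-out already taken from the crude total, which the protocol leaves unclear. Across the readings, the yield runs from about 135,600 to 154,300 WY and power from about 76% to 81%.

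All figures assume even monthly recruitment, the protocol's incidence rates and its one-sided 5% basis. No endpoint, margin or analysis is affected. This should be fixed, but it does not invalidate the design.

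**What to change.** 1. Reconcile section 3 (Milestones footnote), section 6.2 and Table 4 on one follow-up rule, and align the end dates with it.
2. Rebuild Table 4 with administrative censoring under that rule. Deduct drop-out once, and state separately how much of the correction is for stopping or switching treatment.
3. Restate expected WY, expected events and achieved power wherever 150,000 WY is presented as the yield of 101,000 women: the abstract, section 6.2.2, section 6.5, and the 7-per-10,000 scenario rows in Tables 2 and 3.
4. Keep Table 2 line 1 (150,426 WY, 151 events) as the requirement for 80% power, and give the achieved power beside it.

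The cost is a recalculation and possibly a slightly lower stated power. No additional enrolment is needed.
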